13.5 Other Recipients of Adverse Event Reports

- 13.5.1** Events that do not meet the criteria for CTEP-AERS reporting ([Section 13.2](#)) should be reported at the end of each cycle using the forms provided in the CRF packet (See [Section 14.1](#)).
- 13.5.2** COG will forward reports and supporting documentation to the Study Chair, to the FDA (when COG holds the IND) and to the pharmaceutical company (for industry sponsored trials).
- 13.5.3** Adverse events determined to be reportable must also be reported according to the local policy and procedures to the Institutional Review Board responsible for oversight of the patient.

13.6 Reporting Secondary AML/MDS

All cases of acute myeloid leukemia (AML) and myelodysplastic syndrome (MDS) that occur in patients following their chemotherapy for cancer must be reported to the NCI Cancer Therapy Evaluation Program (CTEP) via CTEP-AERS and included as part of the second malignant neoplasm reporting requirements for this protocol (see data submission packet). Submit the completed CTEP-AERS report within 14 days of an AML/MDS diagnosis occurring after protocol treatment for cancer.

Secondary Malignancy:

A *secondary malignancy* is a cancer caused by treatment for a previous malignancy (e.g., treatment with investigational agent/intervention, radiation or chemotherapy). A secondary malignancy is not considered a metastasis of the initial neoplasm.

CTEP requires all secondary malignancies that occur following treatment with an agent under an NCI IND/IDE be reported via CTEP-AERS. Three options are available to describe the event:

- 1) Leukemia secondary to oncology chemotherapy (e.g., acute myelocytic leukemia [AML])
- 2) Myelodysplastic syndrome (MDS)
- 3) Treatment-related secondary malignancy.

Any malignancy possibly related to cancer treatment (including AML/MDS) should also be reported via the routine reporting mechanisms outlined in each protocol.

Second Malignancy:

A *second malignancy* is one unrelated to the treatment of a prior malignancy (and is **NOT** a metastasis from the initial malignancy). Second malignancies require **ONLY** routine reporting via CDUS unless otherwise specified.

13.7 **Reporting Pregnancy, Pregnancy Loss, and Death Neonatal**

When submitting CTEP-AERS reports for “Pregnancy”, “Pregnancy loss”, or “Neonatal loss”, the Pregnancy Information Form should be completed and emailed to the ADV1514 COG Study Assigned Research Coordinator along with any additional medical information ([Appendix III](#)). The potential risk of exposure of the fetus to the investigational agent should be documented in the “Description of Event” section of the CTEP-AERS report.

13.7.1 Pregnancy

- Patients who become pregnant on study risk intrauterine exposure of the fetus to agents which may be teratogenic. For this reason, pregnancy occurring on study or within 6 months following the last dose of study therapy should be reported in an expedited manner via CTEP-AERS as Grade 3 “Pregnancy, puerperium and perinatal conditions - Other (Pregnancy) under the Pregnancy, puerperium and perinatal conditions SOC and reported as Grade 3.
- Pregnancy should be followed until the outcome is known. If the baby is born with a birth defect or anomaly, then a second CTEP-AERS report is required.

13.7.2 Fetal Death

- Pregnancy loss is defined in CTCAE version 5.0 as “Death in utero.”
- Any pregnancy loss should be reported expeditiously, as Grade 4 “Pregnancy loss” under the Pregnancy, puerperium and perinatal conditions SOC. Do NOT report a pregnancy loss as a Grade 5 event since CTEP-AERS recognized any Grade 5 event as a patient death.

13.7.3 Death Neonatal

- Neonatal death, defined in CTCAE version 5.0 as “Newborn deaths occurring during the first 28 days after birth” that is felt by the investigator to be at least possibly due to the investigational agent/intervention, should be reported expeditiously.

- A neonatal death should be reported expeditiously as “Death neonatal” under the “general disorders and administration” SOC when the death is the result of a patient pregnancy or pregnancy in partners of men on study.
- Neonatal death should NOT be reported as “Death neonatal” under the General disorders and administration SOC, a Grade 5 event. If reported as such, the CTEP-AERS interprets this as a death of the patient being treated.

Pregnancy should be followed up until the outcome of the pregnancy is known at intervals deemed appropriate by her physicians. The “Pregnancy Information Form” should be used for all necessary follow-ups. This form is available at http://ctep.cancer.gov/protocolDevelopment/electronic_applications/docs/PregnancyReportForm.pdf.

14.0 RECORDS, REPORTING, AND DATA AND SAFETY MONITORING PLAN

14.1 Categories of Research Records

Research records for this study can be divided into three categories

1. Non-computerized Information: Roadmaps, Pathology Reports, Surgical Reports. These forms are uploaded into RAVE.
2. Reference Labs, Biopathology Reviews, and Imaging Center data: These data accompany submissions to these centers, which forward their data electronically to the COG Statistics & Data Center.
3. Computerized Information Electronically Submitted: All other data will be entered in RAVE with the aid of schedules and worksheets (essentially paper copies of the OPEN and RAVE screens) provided in the case report form (CRF) packet.

See separate CRF Packet, which includes submission schedule.

14.2 Access to Rave for Data Submission/Data Reporting

Data collection for this study will be done through the Medidata Rave clinical data management system. Access to the trial in Rave is granted through the iMedidata application to all persons with the appropriate roles assigned in Regulatory Support System (RSS). To access Rave via iMedidata, the site user must have an active CTEP-IAM account (check at <https://ctepcore.nci.nih.gov/iam/index.jsp>) and the appropriate Rave role (Rave CRA, Read-Only, Site Investigator) on either the COG or PEP-CTN roster at the enrolling site.

Upon initial site registration approval for the study in RSS, all persons with Rave roles assigned on the appropriate roster will be sent a study invitation e-mail from iMedidata. To accept the invitation, site users must log into the Select Login (<https://login.imedidata.com/selectlogin>) using their CTEP-IAM user name and password, and click on the “accept” link in the upper right-corner of the iMedidata page. Please note, site users will not be able to access the study in Rave until all required Medidata and study specific trainings are completed. Trainings will be in the form of electronic learnings (eLearnings), and can be accessed by clicking on the link in the upper right pane of the iMedidata screen.

Users that have not previously activated their iMedidata/Rave account at the time of initial site registration approval for the study in RSS will also receive a separate invitation from iMedidata to activate their account. Account activation instructions are located on the CTSU website, Rave tab under the Rave resource materials (Medidata Account Activation and Study Invitation Acceptance). Additional information on iMedidata/Rave is available on the CTSU members' website under the Rave tab at www.ctsu.org/RAVE/ or by contacting the CTSU Help Desk at [name] or by e-mail at [contact], or by email to the COG Study Assigned Data Manager.

14.3 CDUS

This study will be monitored by the Clinical Data Update System (CDUS) version 3.0. Cumulative protocol- and patient-specific CDUS data will be submitted electronically to CTEP on a quarterly basis by FTP burst of data. Reports are due January 31, April 30, July 31 and October 31. Instructions for submitting data using the CDUS can be found on the CTEP Web site (<http://ctep.cancer.gov/reporting/cdus.html>).

Note: If this study has been assigned to CDUS-Complete reporting, **all** adverse events (both routine and expedited) that have occurred on the study and meet the mandatory CDUS reporting guidelines must be reported via the monitoring method identified above. If this study has been assigned to CDUS-abbreviated reporting, no adverse event reporting (routine or expedited) is required to be reported via CTEP-AERS.

This is not a responsibility of institutions participating in this trial.

14.4 Data and Safety Monitoring Plan

Data and safety is ensured by several integrated components including the COG Data and Safety Monitoring Committee.

14.4.1 Data and Safety Monitoring Committee

This study will be monitored in accordance with the Children's Oncology Group policy for data and safety monitoring of Phase 1 and 2 studies. In brief, the role of the COG Data and Safety Monitoring Committee is to protect the interests of patients and the scientific integrity for all Phase 1 and 2 studies. The DSMC consists of a chair; a statistician external to COG; one external member; one consumer representative; the lead statistician of the PEP-CTN scientific committee; and a member from the NCI. The DSMC meets at least every 6 months to review current study results, as well as data available to the DSMC from other related studies. Approximately 6 weeks before each meeting of the Phase 1 and 2 DSMC, study chairs will be responsible for working with the study statistician to prepare study reports for review by the DSMC. The DSMC will provide recommendations to the COG PEP-CTN Chair and the Group Chair for each study reviewed to change the study or to continue the study unchanged. Data and Safety Committee reports for institutional review boards can be prepared using the public data monitoring report as posted on the COG Web site.

APPENDIX I: PERFORMANCE STATUS SCALES/SCORES

Karnofsky		Lansky	
Score	Description	Score	Description
100	Normal, no complaints, no evidence of disease	100	Fully active, normal.
90	Able to carry on normal activity, minor signs or symptoms of disease.	90	Minor restrictions in physically strenuous activity.
80	Normal activity with effort; some signs or symptoms of disease.	80	Active, but tires more quickly
70	Cares for self, unable to carry on normal activity or do active work.	70	Both greater restriction of and less time spent in play activity.
60	Required occasional assistance, but is able to care for most of his/her needs.	60	Up and around, but minimal active play; keeps busy with quieter activities.
50	Requires considerable assistance and frequent medical care.	50	Gets dressed, but lies around much of the day; no active play, able to participate in all quiet play and activities.
40	Disabled, requires special care and assistance.	40	Mostly in bed; participates in quiet activities.
30	Severely disabled, hospitalization indicated. Death not imminent.	30	In bed; needs assistance even for quiet play.
20	Very sick, hospitalization indicated. Death not imminent.	20	Often sleeping; play entirely limited to very passive activities.
10	Moribund, fatal processes progressing rapidly.	10	No play; does not get out of bed.

APPENDIX II: CORRELATIVE STUDIES GUIDE

Correlative Study	Appendix	Sample Volume		Tube Type
		Volume per sample	Total Cycle 1 and Cycle 2	
Pharmacokinetic Study (PK)	XI-A and XI-B	2 ml	48 ml	Preservative-free heparin (green top)
Tumor Tissue (Required) See Section 8.4 for details	XII	-	-	-
Total Blood Volume			48 ml	

APPENDIX III: PREGNANCY INFORMATION FORM

Attach to CTEP-AERS 5-Day Report

PREGNANCY INFORMATION FAX FACSIMILE TRANSMISSION		Study #:	
Ticket Number: _____		SAF [contact]	
		ALTERNATE [contact]	
Initial Report Date:   -   -  		Follow-up Report Date:   -   -  	
Principal Investigator:		Reporter:	
Reporter Telephone #:		Reporter FAX #:	
Investigator Number:             Subject Number:             Complete all of the investigator and subject number boxes provided. Use leading zeros, when necessary, to complete all expected boxes. Example: Investigator #407 would be filled in as:            		Subject Initials:       Record the first letter of the subject's first, middle and last name, in that sequence. If the subject has no middle name, enter a dash. Example:   -   -  	
Subject's Sex:  Female  Male	Subject's Weight: _____ kg	Subject's Date of Birth:   -   -    	
Subject's Ethnicity (check one only):  Hispanic or Latino  Not Hispanic or Latino  Not Available			
Subject's Race (check all that apply):  American Indian or Alaska Native  Asian  Black or African American  Native Hawaiian or Other Pacific Islander  White  Not Available			
Study Drug:	Study Drug Start Date:   -   -  		
	Study Drug Stop Date:   -   -   OR  Study Drug Continuing		
Dose:	Route:	Frequency:	Kit #:
First Day of Last Menstrual Period:   -   -  		Estimated Date of Delivery:   -   -  	
Method of Contraception (check all that apply):  Oral Contraceptive Pills  Condoms  Periodic Abstinence  Progestin Injection or Implants  Spermicide  Diaphragm  Intrauterine Device (IUD)  Tubal Ligation  Other, specify: _____			
Reproductive History:  Gravida _____  Para _____			
Tests performed during pregnancy:  None  Unknown  CVS Results:  Normal  Abnormal  Amniocentesis Results:  Normal  Abnormal  Ultrasound Results:  Normal  Abnormal			
Pregnancy Outcome Was pregnancy interrupted?  Yes  No If yes, specify:  Elective Termination  Spontaneous Abortion  Ectopic Date of Termination:   -   -   If pregnancy was not terminated, specify pregnancy outcome (and provide infant outcome information)  Vaginal Birth:  Premature  Term OR  C-Section:  Scheduled  Emergency Date of Delivery:   -   -   Infant outcome information:  Normal  Abnormal			
Additional Case Details (if needed):			

NOTE: For initial reporting email both the Pregnancy CTEP-AERS Report and this additional Pregnancy Information Form to the ADVL1514 COG Study Assigned Research Coordinator. For follow-up reporting, email only this Pregnancy Information Form to the ADVL1514 COG Study Assigned Research Coordinator (See [Section 13.7](#)).

APPENDIX IV: TEMOZOLOMIDE DOSING NOMOGRAM FOR TEMOZOLOMIDE 125 MG/M²/DOSE

Temozolomide dose assignment: 125 mg/m²

BSA (m ²)	Administered daily dose (mg)
0.2-0.49*	4.17 mg/kg*
0.50-0.53	65
0.54-0.59	70
0.60-0.65	80
0.66-0.69	85
0.70-0.75	90
0.76-0.81	100
0.82-0.85	105
0.86-0.91	110
0.92-0.97	120
0.98-1.01	125
1.02-1.07	130
1.08-1.15	140
1.16-1.23	150
1.24-1.31	160
1.32-1.39	170
1.40-1.47	180
1.48-1.55	190
1.56-1.67	200
1.68-1.83	220
1.84-1.95	240
1.96-2.00	250
> 2.0	250

*Dosing for patients with BSA <0.5 m² is by mg/kg, rounded to the nearest 5 mg

APPENDIX V: INSTRUCTIONS FOR TEMOZOLOMIDE PREPARATION, ADMINISTRATION AND SAFE HANDLING FOR PATIENTS WHO ARE UNABLE TO SWALLOW CAPSULES

Patient Name: _____ **Cycle#:** _____ **Date Range:** _____

Temozolomide is an oral medicine for the treatment of cancer. This information sheet will help you prepare, administer, store, and dispose of the medicine. Please read the information before preparing and giving the medicine. If you have any questions, please contact: _____

WHAT DO I NEED?

Your Temozolomide dose is: _____ mg
You should use the following number of capsules for each dose:

Number of temozolomide capsules per dose					
5 mg	20 mg	100 mg	140 mg	180 mg	250 mg

Give each dose by mouth one time each morning for 5 days in a row

You should take the temozolomide on the following days: _____

Supplies:

- Temozolomide capsules (see the table above)
- Disposable pad or paper towels
- Disposable gloves and mask and a pair of goggles (eye protection)
- Disposable cup and disposable spoon
- A container to collect waste (zip top plastic bag or medical waste bag or container)
- A small amount of applesauce or apple juice
 - Two teaspoons (10 mL) should be enough. A single-serving container of applesauce may be used, but the patient must be able to eat the entire contents of the container to ensure the full dose is taken.
 - Food should be cool or close to room temperature when administered; do not use hot or boiling food

HOW DO I STORE THE MEDICINE AND WASTE?

Store the medication in the original bottle away from food and out of the reach of children or pets. Store the waste container out of the reach of children or pets. Return the container to the clinic during your next visit.

WHAT SAFETY MEASURES SHOULD I TAKE?

APPENDIX IX: MEDICATION DIARY

COG Patient ID: _____ **ACC # :** _____ **Institution :** _____

Please do not write patient names on this form.

Course #: _____

For each day, fill in the **date and time** temozolomide, irinotecan, and cefixime (or equivalent antibiotic to prevent diarrhea) were given. Irinotecan should be given one hour after administration of temozolomide. Make note of other drugs and supplements taken. Cefixime or an available equivalent antibiotic will be used as diarrheal prophylaxis. Initiation of antibiotic treatment at least two days prior to the start of irinotecan is recommended. This antibiotic therapy should continue throughout protocol therapy. Return the completed diary to your institution after each treatment course.

PLEASE CAREFULLY READ THE STEPS FOR DRUG ADMINISTRATION (SEE [RECOMMENDATIONS FOR ADMINISTRATION OF TEMOZOLOMIDE](#) AND [PARENT GUIDELINES FOR ADMINISTRATION OF ORAL IRINOTECAN](#)) BEFORE GIVING DRUGS.

Day:						
						Date: _____ Cefixime Time: _____ Dose: _____
Date: _____ Cefixime Time: _____ Dose: _____	Date: _____ Temozolomide, Irinotecan, ABI-009 given in Clinic. DO NOT TAKE AT HOME Cefixime Time: _____ Dose: _____	Date: _____ Temozolomide Time: _____ Dose: _____ Irinotecan Time: _____ Dose: _____ Cefixime Time: _____ Dose: _____	Date: _____ Temozolomide Time: _____ Dose: _____ Irinotecan Time: _____ Dose: _____ Cefixime Time: _____ Dose: _____	Date: _____ Temozolomide Time: _____ Dose: _____ Irinotecan Time: _____ Dose: _____ Cefixime Time: _____ Dose: _____	Date: _____ Temozolomide Time: _____ Dose: _____ Irinotecan Time: _____ Dose: _____ Cefixime Time: _____ Dose: _____	Date: _____ Cefixime Time: _____ Dose: _____
Date: _____ Cefixime Time: _____ Dose: _____	Date: _____ ABI-009 given in Clinic Cefixime Time: _____ Dose: _____	Date: _____	Date: _____	Date: _____	Date: _____	Date: _____
Date: _____	Date: _____	Date: _____	Date: _____	Date: _____	Date: _____	Date: _____ Cefixime Time: _____ Dose: _____
Date: _____ Cefixime Time: _____ Dose: _____						
NOTES:						

**APPENDIX X: UNACCEPTABLE ENZYME-INDUCING AND RECOMMENDED NON-ENZYME
INDUCING ANTICONVULSANTS**

Recommended Non-enzyme inducing anticonvulsants
Clonazepam
Diazepam
Ethosuximide
Ezogabine
Gabapentin
Lacosamide
Lamotrigine
Levetiracetam
Lorazepam
Perampanel
Tiagabine
Topiramate
Valproic Acid
Zonisamide
Unacceptable Enzyme inducing anticonvulsants
Carbamazepine
Felbamate
Phenobarbital
Fosphenytoin
Phenytoin
Primidone
Oxcarbazepine

APPENDIX XI-A: PHARMACOKINETIC STUDY FORM FOR ABI-009

COG Pt ID # _____ Cycle 1, Day 1 Date: _____ Please do not
write patient names on this form or on samples.

Patient Weight: _____ kg Body Surface Area: _____ m²

ABI-009 Dose Level: _____ mg/m² ABI-009 Total Daily Dose: _____ mg

ABI-009 Sampling Schedule during Cycle 1 (Single Agent) and Cycle 2 (Combination Therapy):

Blood samples (2 ml) will be collected in EDTA tubes (lavender top) at the following time points: Day 1 (pre-infusion, end of infusion, 1 hr., 2 hrs., 4 hrs., and 8 hrs. after beginning the infusion), Day 2 (24 hrs. after beginning the Day 1 infusion), Day 4 (72 hrs. [± 24 hrs.] after beginning the Day 1 infusion), Day 8 (pre-infusion) of Cycle 1 and 2.

Record the exact time the sample is drawn along with the exact time ABI-009 is given on Days 1 and 8.

Blood Sample No.	Time Point	Scheduled Collection Time	Actual Date Sample Collected	Actual Time Sample Collected (24-hr clock)
1	Cycle 1, Day 1	Prior to Day 1 ABI-009 infusion	___/___/___	__:__:__
ABI-009 Infusion on Day 1 Date: ___/___/___ Start Time: ___:___:___ Stop Time: ___:___:___				
2	Cycle 1, Day 1	30 min. after beginning Day 1 ABI-009 infusion	___/___/___	__:__:__
3	Cycle 1, Day 1	1 hr. after beginning Day 1 ABI-009 infusion	___/___/___	__:__:__
4	Cycle 1, Day 1	2 hrs. after beginning Day 1 ABI-009 infusion	___/___/___	__:__:__
5	Cycle 1, Day 1	4 hrs. after beginning Day 1 ABI-009 infusion	___/___/___	__:__:__
6	Cycle 1, Day 1	8 hrs. after beginning Day 1 ABI-009 infusion	___/___/___	__:__:__
7	Cycle 1, Day 2	24 hrs. after beginning Day 1 ABI-009 infusion	___/___/___	__:__:__
8	Cycle 1, Day 4	72 hrs. (± 24 hrs.) after beginning Day 1 ABI-009 infusion	___/___/___	__:__:__
9	Cycle 1, Day 8	Prior to Day 8 ABI-009 infusion	___/___/___	__:__:__
ABI-009 Infusion on Day 8 Date: ___/___/___ Start Time: ___:___:___ Stop Time: ___:___:___				
10	Cycle 2, Day 1	Prior to Day 1 ABI-009 infusion	___/___/___	__:__:__
ABI-009 Infusion on Day 1 Date: ___/___/___ Start Time: ___:___:___ Stop Time: ___:___:___				
11	Cycle 2, Day 1	30 min. after beginning Day 1 ABI-009 infusion	___/___/___	__:__:__
12	Cycle 2, Day 1	1 hr. after beginning Day 1 ABI-009 infusion	___/___/___	__:__:__
13	Cycle 2, Day 1	2 hrs. after beginning Day 1 ABI-009 infusion	___/___/___	__:__:__

14	Cycle 2, Day 1	4 hrs. after beginning Day 1 ABI-009 infusion	___/___/___	:
15	Cycle 2, Day 1	8 hrs. after beginning Day 1 ABI-009 infusion	___/___/___	:
16	Cycle 2, Day 2	24 hrs. after beginning Day 1 ABI-009 infusion	___/___/___	:
17	Cycle 2, Day 4	72 hrs. (± 24 hrs.) after beginning Day 1 ABI-009 infusion	___/___/___	:
18	Cycle 2, Day 8	Prior to Day 8 ABI-009 infusion	___/___/___	:
ABI-009 Infusion on Day 8 Date: ___/___/___ Start Time: : Stop Time: : 				

One copy of this Pharmacokinetic Study Form should be uploaded into RAVE. A second copy should be sent with the samples to the address listed in [Section 8.3.6](#). See [Section 8.3](#) for detailed guidelines for packaging and shipping PK samples.

Signature: _____
(site personnel responsible for sample collection)

Date: _____

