1.0 GOALS AND OBJECTIVES (SCIENTIFIC AIMS)

1.1 Primary Aims

- 1.1.1 To estimate the maximum tolerated dose (MTD) and/or recommended Phase 2 dose (RP2D) of ABI-009 administered as an intravenous infusion over 30 minutes on Days 1 and 8 of a 21-day cycle, in combination with temozolomide and irinotecan (administered on Days 1-5) in pediatric patients with recurrent or refractory solid tumors, including CNS tumors.
- 1.1.2 To define and describe the toxicities of single-agent ABI-009 administered as an intravenous infusion over 30 minutes on Days 1 and 8 of a 21-day cycle in pediatric patients with recurrent or refractory solid tumors, including CNS tumors.
- 1.1.3 To define and describe the toxicities of ABI-009 administered as an intravenous infusion over 30 minutes on Days 1 and 8 of a 21-day cycle in combination with temozolomide and irinotecan (administered on Days 1-5) in pediatric patients with recurrent or refractory solid tumors, including CNS tumors.
- 1.1.4 To characterize the pharmacokinetics of ABI-009 in pediatric patients with recurrent or refractory solid tumors, including CNS tumors.

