5.0 TREATMENT PROGRAM

5.1 Overview of Treatment Plan

Cycle 2+ Combination Therapy 21 Day Duration					
Day -2	Cefixime				PJP Prophylaxis
Day -1					
Day 1		TEMO	IRIN	ABI-009	
Day 2		TEMO	IRIN		
Day 3		TEMO	IRIN		
Day 4		TEMO	IRIN		
Day 5		TEMO	IRIN		
Day 6					
Day 7					
Day 8				ABI-009	
Day 9-19					
Day 20 ¹	Cefixime				
Day 21 ²		Evaluation			

TEMO: Temozolomide
 IRIN: Irinotecan
 PJP: Pneumocystis pneumonia

¹ Day 20 equals Day -2 of the following cycle.

² Day 21 equals Day -1 of the following cycle.

A cycle of therapy is considered to be 21 days. A cycle may be repeated for a total of 35 cycles, up to a total duration of therapy of approximately 24 months.

Drug doses should be adjusted based on the BSA calculated from height and weight measured within 7 days prior to the beginning of each cycle.

5.1.1 Cycle 1

Pre-Amendment #4: ABI-009 will be administered intravenously over 30 minutes on Days 1 and 8 of Cycle 1 (beginning at Dose Level 1 = 35 mg/m²/dose; see dose escalation table in [Section 5.3.1](#)). The use of in-line filters is NOT necessary. Upon completion of infusion, the infusion catheter should be flushed with normal saline.

Amendment #4: ABI-009 will be administered intravenously over 30 minutes on Days 1 and 8 of Cycle 1 (beginning at Dose Level -2 = 15 mg/m²/dose; see dose escalation table in [Section 5.3.1](#)). The use of in-line filters is NOT necessary. Upon completion of infusion, the infusion catheter should be flushed with normal saline.

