8.3.2 Sampling Schedule (See [Appendix XI-A](#) and [Appendix XI-B](#))

Whole blood samples (2 ml) will be obtained prior to drug administration and at the following time points:

8.3.2.1 ABI-009 Sampling Schedule during Cycle 1 (Single Agent) and Cycle 2 (Combination Therapy):

- Day 1: Pre-dose, end of infusion, and then 1, 2, 4, and 8 hrs after beginning of infusion.
- Day 2: 24 hours post-Day 1 ABI-009 dose.
- Day 4 (\pm 1 day): 72 hours (\pm 24 hours) post- Day 1 ABI-009 dose
- Day 8: Pre-ABI-009 dose.

8.3.2.2 Irinotecan/SN-38 Sampling Schedule during Cycle 2 (Combination Therapy):

- Day 1: Pre-dose, and then 10 min, 1 hr, 3 hrs, and 6 hrs post-irinotecan dose.
- Day 2: Pre-Day 2 irinotecan dose (24 hours after Day 1 irinotecan dose).

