8.3.3 Sample Collection and Handling Instructions

8.3.3.1 ABI-009

Blood samples (2 ml) will be collected in EDTA tubes at a site distant from the infusion for pharmacokinetic evaluation. Samples cannot be drawn from the 2nd lumen of a multi-lumen catheter through which drug is being administered. Record the exact time that the sample is drawn along with the exact time that the infusion is started and stopped.

If the duration of infusion is changed, the sample should be collected immediately before termination of the infusion.

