11.5 Pharmacokinetic and Correlative Studies and Response Analysis

A descriptive analysis of pharmacokinetic (PK) parameters of ABI-009 as a single agent and in combination with temozolomide and irinotecan will be performed to define systemic exposure, drug clearance, and other pharmacokinetic parameters. The PK parameters will be summarized with simple summary statistics, including means, medians, ranges, and standard deviations (if numbers and distribution permit).

While the primary aim of this study is to evaluate the toxicity of ABI-009, patients will have disease evaluations performed as indicated in [Section 8.1](#). Disease response will be assessed according to RECIST criteria for patients with solid tumors, and will be reported descriptively.

All these correlative biology study analyses will be descriptive and exploratory and hypotheses generating in nature.

¹These distributions are based on historical Phase 1 enrollments.

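### Two rows of the ABI-009 sampling form time the peak sample by the clock rather than by the end of infusion, which risks a low Cmax when an infusion does not last 30 minutes

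*Combined protocol and SAP*

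**What the plan says.** Section 5.1.1 sets the infusion length: "ABI-009 will be administered intravenously over 30 minutes on Days 1 and 8 of Cycle 1". Section 5.1.2 gives the same 30 minutes for later cycles.

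Four places set the time of the peak sample:

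- Section 8.3.2.1: "Day 1: Pre-dose, end of infusion, and then 1, 2, 4, and 8 hrs after beginning of infusion".
- Section 8.3.3.1: "If the duration of infusion is changed, the sample should be collected immediately before termination of the infusion".
- Appendix XI-A, introduction above the table: "Day 1 (pre-infusion, end of infusion, 1 hr., 2 hrs., 4 hrs., and 8 hrs. after beginning the infusion".
- Appendix XI-A, scheduled collection time for samples 2 (Cycle 1) and 11 (Cycle 2): "30 min. after beginning Day 1 ABI-009 infusion".

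Section 8.3.3.1 also requires actual times: "Record the exact time that the sample is drawn along with the exact time that the infusion is started and stopped". The form has fields for them.

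Pharmacokinetics is primary aim 1.1.4: "To characterize the pharmacokinetics of ABI-009 in pediatric patients with recurrent or refractory solid tumors, including CNS tumors". Section 11.5 plans a descriptive analysis "to define systemic exposure, drug clearance, and other pharmacokinetic parameters". Neither place names Cmax, but Section 2.6 reports it from this trial (Dose Level -1: mean 374 µg/L, CV 39%).

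**The concern.** Three of the four places define the sample by an event, the end of the infusion. The two table rows define it by the clock. The rows sit next to the box where staff enter the draw time, so they are the instruction most likely to be read at the bedside. The form does not repeat the rule for a changed infusion length, and where it refers to Section 8.3 for detailed guidance, it does so for packaging and shipping.

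The definitions part company only when the infusion does not last 30 minutes, which is the case Section 8.3.3.1 foresees. A draw at 30 minutes is then too early (longer infusion) or too late (shorter infusion), and the next sample is at 1 hour. Recorded times can show afterwards that a peak was missed, but they do not supply the missing concentration. With 6 evaluable patients at Dose Level -2 and up to 6 more in the pharmacokinetic expansion (Sections 11.1.1 and 11.3.1), a few mistimed peaks could move a mean Cmax.

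**Working it through.** **1. Is it one sample or two?** Appendix XI-A lists 9 ABI-009 samples per cycle for two cycles, and Appendix XI-B lists 6 irinotecan samples. 9 × 2 + 6 = 24 samples, and 24 × 2 ml = 48 ml, which is the total in Appendix II. The end-of-infusion and 30-minute labels therefore name the same sample.

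**2. As planned.** With a 30-minute infusion, the end of infusion is 30 minutes after the start. The labels agree and the shortfall is 0%.

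**3. Off plan, if the row is followed.** The plan gives no figure to reproduce here, so this is an illustration.

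- Model: constant-rate infusion over T minutes, one compartment, first-order loss at rate k = ln 2 / h.
- Assumed: early half-life h of 10, 20, 30 or 60 minutes. The documents give only the adult half-life of 40-91 hours (Section 2.3.3), which does not describe the first hour.
- The true peak is at time T. Relative to it:
  - a sample at t ≤ T reads (1 − e^(−kt)) / (1 − e^(−kT));
  - a sample at t > T reads e^(−k(t−T)).
- Observed Cmax is the highest sample, so the larger of the 30-minute and 1-hour readings is used.

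Example: T = 45, h = 60. The 30-minute sample reads (1 − 2^(−0.5)) / (1 − 2^(−0.75)) = 0.72. The 1-hour sample reads 2^(−0.25) = 0.84. Observed Cmax is 84% of the peak, not 72%.

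| Infusion (min) | h = 10 | h = 20 | h = 30 | h = 60 | Shortfall |
|---|---|---|---|---|---|
| 25 | 0.71 | 0.84 | 0.89 | 0.94 | 6-29% |
| 28 | 0.87 | 0.93 | 0.95 | 0.98 | 2-13% |
| 30 | 1.00 | 1.00 | 1.00 | 1.00 | 0% |
| 32 | 0.98 | 0.96 | 0.96 | 0.95 | 2-5% |
| 40 | 0.93 | 0.86 | 0.83 | 0.79 | 7-21% |
| 45 | 0.92 | 0.82 | 0.77 | 0.84 | 8-23% |
| 60 | 1.00 | 1.00 | 1.00 | 1.00 | 0% |

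Entries are observed Cmax divided by true peak. At 45 minutes a finer search over h from 10 to 60 reaches 24.5%, near h = 37. At 60 minutes the 1-hour sample falls at the end of infusion and catches the peak.

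**4. Sensitivity to the model.** A second set of cases used the 63-hour adult terminal half-life, either alone or with an assumed distribution phase (half-life 5 to 60 minutes, weight 0.50 to 0.95). The shortfall was 0.1-42% at 25 minutes, 0.4-19% at 40 minutes, 0.3-23.5% at 45 minutes and 0% at 30 or 60 minutes. The direction holds, but the size is not known.

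**5. Effect on AUC and clearance.** In a linear trapezoid with neighbours at 0 and 1 hour, the 30-minute sample has weight (1 − 0)/2 = 0.5 h. Take the 29% case and the Section 2.6 values for Dose Level -1: 0.29 × 374 = 108 µg/L, and 0.5 × 108 = 54 µg·h/L. Against the mean AUCinf of 10113 µg·h/L this is 54 / 10113 = 0.5%. Clearance, dose divided by AUC, moves by about the same amount.

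**The case against.** The strongest reply is that the protocol already handles this. The infusion is planned for 30 minutes throughout, Section 8.3.3.1 says what to do if that changes, and the form's introduction says end of infusion. A site would have to overlook both for the error to occur. Infusion start, infusion stop and draw times are all recorded, so mistimed samples can be found. Cmax is not named in aim 1.1.4 or Section 11.5, and the MTD rests on DLT counts (Sections 11.2.2 and 11.3), not on Cmax.

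All of this is correct, and it limits the point. It does not make the rows right: in the one situation Section 8.3.3.1 anticipates, they give a different time from that section.

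A reader might infer that the trial's Cmax values are biased low, or that every infusion not lasting exactly 30 minutes misses the peak. The documents support neither reading. They do not report how long infusions lasted or which instruction sites followed. A 60-minute infusion is caught by the 1-hour sample, and a 32-minute infusion costs only a few percent. Nor do they show added spread or a distorted contrast between Cycle 1 and Cycle 2: the 39% CV is in line with the up to 40% that Section 2.6 cites for adults, and Section 11.5 plans no formal comparison.

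**Conclusion.** The inconsistency is real and lies in Appendix XI-A, rows 2 and 11. It matters only when an infusion runs moderately long or short and staff follow the row. Observed Cmax then tends to be low: about 6-29% at 25 minutes, 7-21% at 40 minutes and up to about 24.5% at 45 minutes, on an assumed early half-life of 10 to 60 minutes and a one-compartment model. It is nil at 30 and 60 minutes. Other assumptions change these figures substantially. AUC and clearance, the exposure measures that Section 11.5 does name, shift by about 0.5% in the example.

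This is a risk to one descriptive parameter. It is not an established bias and not a threat to the primary pharmacokinetic aim as a whole. It is worth correcting because the correction is simple and a missed peak cannot be measured later.

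**What to change.** In Appendix XI-A, change the scheduled collection time for samples 2 and 11 to *End of infusion, immediately before stopping (nominally 30 min.)*. The rows then agree with Sections 8.3.2.1 and 8.3.3.1 and with the form's introduction. The cost is two rows on one form, with no extra sample, visit or data field.

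For samples already drawn, compare the recorded draw time with the recorded stop time to see whether any peak was missed. How to present any such Cmax values can be left to the study team.
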